**It is sufficient that:**

An **incident** associated with a device happened and

Property of Haleon- Confidential

May not be used, divulged, published or otherwise disclosed without the consent of Haleon

- The **incident** was such that, if it occurred again, might lead to death or a serious deterioration in health.
- A serious deterioration in state of health can include any of the following:
  - Life-threatening illness
  - Permanent impairment of body function or permanent damage to body structure
  - Condition necessitating medical or surgical intervention to prevent one of the above
  - Fetal distress, fetal death, or any congenital abnormality or birth defects

**Examples of incidents:**

- A subject, user, caregiver, or healthcare professional is injured as a result of a medical device failure or its misuse.
- A subject's study treatment is interrupted or compromised by a medical device failure.
- A misdiagnosis due to medical device failure leads to inappropriate treatment.
- A subject's health deteriorates due to medical device failure.

### 9.1.11 Reporting of Incidents and Malfunctions

All incidents must be reported to Haleon **immediately and under no circumstance should this exceed 24 hours** of the investigator or designee becoming aware of the situation.

Any medical device incident occurring during the study will be documented in the subject's medical records, if in accordance with the investigator's normal clinical practice, and on the appropriate Incident Report Form. In addition, for incidents fulfilling the definition of an AE (serious and non-serious), the appropriate AE CRF page and SAE form will be completed and reported as per the AE and SAE reporting sections.

The Incident Report Form will be completed as thoroughly as possible and signed by the investigator before transmittal to Haleon. It is very important that the investigator describes any corrective or remedial actions taken to prevent recurrence of the incident.

The completed Incident Report Form should be scanned and emailed to the Case Management Group mailbox **PPD** with copy to the appropriate Study Manager, with the study number and subject number in the subject line of the email **immediately and under no circumstance should this exceed 24 hours** after study site personnel learn of the event. If there is an SAE, the completed SAE form should be sent together with this report form. However, if a copy of the SAE report is sent with this form, this does not replace the procedure to report an SAE. The original Incident Report Form will be retained in the investigator study master file.

The initial report will be followed up with more information as relevant, or as requested by the study manager.

The investigator will follow the following directions regarding the reporting of a device failure (malfunction):

- Notify Haleon immediately (by following the process described above).
- Schedule the subject to return to the site promptly to return the failed device.
- Record any incidents on the CRF and Incident Report Form following instructions given in the section above.

- For any incident/malfunction occurring with a medical device (including those that are part of combination products) supplied by Haleon, return the failed device to the sponsor as soon as possible, including documentation of the details of the failure
- For any incident/malfunction occurring with a medical device (including those that are part of combination products) supplied by the Investigator site, report the incident to the device manufacturer and follow the manufacturer instructions for the return of the failed device (whilst keeping Haleon informed).

### **9.1.12 Follow-up of Medical Device Incidents**

Medical device incidents involving an AE will be followed and reported in the same manner as other AEs. This applies to all subjects, including those who discontinue study product or are withdrawn from the study.

The investigator is responsible for ensuring that follow-up includes any supplemental investigations as indicated to elucidate the nature and/or causality of the incident.

New or updated information will be recorded on the originally completed Incident Report form with all changes signed and dated by the investigator.

### **9.1.13 Regulatory Reporting Requirements for Medical Device Incidents**

To fulfill regulatory reporting obligations worldwide, the investigator is responsible for the detection and documentation of events meeting the definitions of incident or malfunction that occur during all periods of the study in which the medical device is used.

The investigator will promptly report all incidents occurring with any medical device provided for use in the study in order for the sponsor to fulfill the legal responsibility to notify appropriate regulatory authorities and other entities about certain safety information relating to medical devices being used in clinical studies.

The investigator, or responsible person according to local requirements (e.g. the head of the medical institution), will comply with the applicable local regulatory requirements relating to the reporting of incidents to the IRB/IEC.

## **9.2 DISCONTINUATION OF STUDY PRODUCT AND SUBJECT DISCONTINUATION/WITHDRAWAL**

If a subject is discontinued early from the study product (Section 9.2.1) or discontinued or prematurely withdraws from the study (Section 9.2.2), the reason(s) for intervention discontinuation or withdrawal and the associated date must be documented in the relevant section(s) of the CRF. If a subject is discontinued early from the study product, the subject should stay in the study and complete the remaining assessments unless they need to be withdrawn (see Section 9.2.2).

### **9.2.1 Discontinuation of Study Product**

A subject may be discontinued from the study product at any time whilst still in the study at the discretion of the investigator related to safety, subject consent or a potential worsening of the risk / benefit assessment from the subject of remaining on the intervention for the following reasons:

- Adverse Event
- Lack of efficacy from the intervention

Property of Haleon- Confidential

May not be used, divulged, published or otherwise disclosed without the consent of Haleon

- Subject request
- Subject to be withdrawn from the study (see Section **9.2.2**)

### **9.2.2 Subject Discontinuation/Withdrawal**

A subject may withdraw from the study at any time at his or her own request or may be withdrawn at any time at the discretion of the investigator or sponsor for safety, behavioral reasons, or the inability of the subject to comply with the protocol-required schedule of study visits or procedures.

The following circumstances require discontinuation of study product and/or premature subject withdrawal:

- Protocol violation that may impact the subject's safety
- Withdrawal of informed consent
- Subject lost to follow-up
- Unblinding of the subject
- Pregnancy

If the subject withdraws from the study and withdraws consent for disclosure of future information, no further evaluations should be performed, and no additional data should be collected. The sponsor may retain and continue to use any data collected before such withdrawal of consent.

### **9.2.3 Lost to Follow up**

If a subject fails to return to the site for a required study visit, the investigator or designee must make every effort to regain contact with the subject (where possible, 3 telephone calls or emails or local equivalent methods) and reschedule the missed visit as soon as possible and counsel the subject on the importance of maintaining the assigned visit schedule and ascertain whether the subject wishes to and/or should continue in the study.

A subject will be considered lost to follow up and withdrawn from the study if he or she repeatedly fails to return for scheduled visits and is unable to be contacted by the study site.

If contact is made with the subject, the investigator should inquire about the reason for withdrawal, request that the subject return all products that they had been dispensed and if appropriate request that the subject return for a final visit and follow-up with the subject regarding any unresolved adverse events (AEs).

## **9.3 Data Management**

As used in this protocol, the term CRF is understood to refer to either a paper form or an electronic data record or both, depending on the data collection method.

The source documents which contain the source of data recorded in the CRF should be specified. The CRF can be used as a source document at the discretion of data management.

Each subject will be assigned and identified by a unique Screening Subject Number. Any reference made to an individual subject within the study must be done using their unique Screening Subject Number.

Property of Haleon- Confidential

May not be used, divulged, published or otherwise disclosed without the consent of Haleon

### 9.3.1 Case Report Form

A CRF is a printed, optical, or electronic document designed to record the protocol required information to be reported to the sponsor on each trial subject.

For each subject who has given informed consent/assent the CRF must be completed and signed by the Principal Investigator (or authorized designee) to certify that the data are complete and correct. The investigator must maintain accurate documentation (source data) that supports the information entered in the CRF.

### 9.3.2 Data Handling

Documentation of all data management activities should allow step-by-step retrospective assessment of data quality and study performance.

Any changes or corrections to data will be tracked and will include the rationale for the change. A complete record of the changes and corrections will be endorsed by the Investigator.

### 9.3.3 Data Queries

Reports and listings on the CRF data will be run and manual queries will be raised as needed for site clarification or correction.

The study monitor will perform ongoing review of the CRFs in accordance with the monitoring plan, to confirm that data entered into the CRF by authorized site personnel are accurate, complete, and verifiable from source documents; that the safety and rights of participants are being protected; and that the study is being conducted in accordance with the currently approved protocol and any other study agreements. For this study not all elements of ICH GCP will be applied.

## 9.4 Processing Patient Reported Outcomes

Paper based patient reported outcome (PRO) data (eg study questionnaires) will be entered into the CRF

All PRO source data should be reviewed by the study staff and the study monitor to ensure accurate transcription of data and that any potential AEs or concomitant medications reported on these documents are discussed with the subject and transcribed accurately to the CRF. PROs that are classed as source data will be retained by the investigator and true/certified copies may be sent to a designated vendor or Haleon as required. Any AEs or concomitant medications collected as PRO will be reviewed and transcribed to the CRF by the site.

To protect the privacy of subjects, no Personal Information (PI) (including the subject's name or initials or birth date) is to be recorded on any PRO Data that will be forwarded to Haleon or Third-Party Vendor.

## 9.5 Regulatory and Ethical Considerations

### 9.5.1 Institutional Review Board/ Ethics Committee

It is the responsibility of the investigator to have prospective approval of the study protocol, protocol amendments, informed consent document, investigator brochure/safety statement (including any updates) and other relevant documents, e.g. recruitment advertisements, if applicable, from the IRB/EC. All correspondence with the IRB/EC should be retained in the

Property of Haleon- Confidential

May not be used, divulged, published or otherwise disclosed without the consent of Haleon

investigator file. Copies of IRB/EC approvals should be forwarded to Haleon prior to the initiation of the study, and also when subsequent amendments to the protocol are made.

The only circumstance in which an amendment may be initiated prior to IRB/EC approval is where the change is necessary to eliminate apparent immediate hazards to the subjects. In that event, the investigator must notify the IRB/EC and Haleon in writing immediately after the implementation.

### **9.5.2 Ethical Conduct of the Study**

The study will be conducted in accordance with the protocol and legal and regulatory requirements, as well as the general principles set forth in the International Ethical Guidelines for Biomedical Research Involving Human Subjects ([Council for International Organizations of Medical Sciences, 2002](#)), International Ethical Guidelines for Health-Related Research Involving Humans, guidelines for GCP ([Council for International Organizations of Medical Sciences, 2016](#), [ICH, 1996](#)), and the Declaration of Helsinki ([World Medical Association, 2013](#)).

In addition, the study will be conducted in accordance with the protocol, the ICH guideline on GCP and ISO 14155:2011, and applicable local regulatory requirements and laws.

### **9.5.3 Subject Information**

All parties will ensure protection of subject personal data and will not include subject names or other identifiable data in any reports, publications, or other disclosures, except where required by laws.

When study data are compiled for transfer to Haleon and other authorized parties, subject names, addresses, and other identifiable data will be replaced by numerical codes based on a numbering system provided by Haleon in order to de-identify study subjects.

The study site will maintain a confidential list of subjects who participated in the study, linking each subject's numerical code to his or her actual identity. In case of data transfer, Haleon will maintain high standards of confidentiality and protection of subjects' personal data consistent with applicable privacy laws.

## **9.6 Records Retention**

Following closure of the study, the investigator must maintain all site study records (except for those required by local regulations to be maintained elsewhere), in a safe and secure location.

Where permitted by local laws/regulations or institutional policy, some or all of these records can be maintained in a format other than hard copy (e.g., microfiche, scanned, electronic); however, caution needs to be exercised before such action is taken.

The investigator must notify Haleon of any changes in the archival arrangements, including, but not limited to, archival at an off-site facility or transfer of ownership of the records in the event the investigator is no longer associated with the site.

## **9.7 Disclosure and Publication Policy**

Study information from this protocol may be posted on publicly available clinical trial registers before enrollment of subjects begins in accordance with applicable Haleon policies.

Haleon intends to make anonymized subject-level data from this study available to external researchers for scientific analyses or to conduct further research that can help advance medical

Property of Haleon- Confidential

May not be used, divulged, published or otherwise disclosed without the consent of Haleon

science. This helps ensure the data provided by study participants are used to maximum effect in the creation of knowledge and understanding.

The procedures and timing for public disclosure of the results summary and for development of a manuscript for publication will be in accordance with sponsor policy and as per the country specific requirements for disclosure.

## 9.8 Abbreviations

The following is a list of abbreviations that may be used in the protocol.

**Table 9-1 Abbreviations**

Abbreviation	Term
AE	adverse event
ANOVA	analysis of variance
BDR	blinded data review
CI	confidence interval
CRF	case report form
DH	Dentine Hypersensitivity
EAR	Erosion, Abrasion, Recession (assessment of)
eCRF	Electronic Case Report Form
FDA	Food and Drug Administration (United States)
GCP	Good Clinical Practice
ICH	International Conference on Harmonisation
IRB	institutional review board
LMS	Labelled Magnitude Scale
LSLV	last subject last visit
MedDRA	medical Dictionary for Regulatory Activities
MGI	Modified Gingival Index
MMRM	Mixed model with repeated measures
N/A	not applicable
OST	Oral Soft Tissue (examination)
OHT	Oral Hard Tissue (examination)
PI	principal investigator
SAE	Serious Adverse Event
USA	United States of America
VAS	Visual Analogue Scale

## 9.9 Study Product Usage Instructions Sheet

### INSTRUCTIONS FOR PRODUCT USE

Brush your teeth twice a day (morning and evening).

Each time you brush:

- Dispense a ribbon of toothpaste covering the length of the toothbrush head (see below picture). Only the supplied toothbrush may be used.

Property of Haleon- Confidential

May not be used, divulged, published or otherwise disclosed without the consent of Haleon

- Set your timer for 1 minutes, and then brush your teeth in your usual manner for 1 timed minute.

- Bring your toothpaste, toothbrush and tooth bleaching kit to all study visits.

#### **Peroxide bleaching usage**

On days where the study staff have indicated you should use your peroxide tooth bleaching kit:

- Apply the peroxide-containing dental trays to your teeth according to the instructions provided by the study site. You should use the peroxide once-per-day for a total of 7 days. If possible try to perform your tooth bleaching at roughly the same time each day. You should place the tray on your teeth and keep the tray in place for 15 minutes (please use the supplied timer). After removing the trays please brush your teeth according to the brushing instructions above. Should you experience any gum soreness or irritation please apply a thin smear of the supplied petroleum jelly to your gums prior to next wearing your trays. Try to avoid getting the petroleum jelly in contact with your teeth.

## 9.10 Tooth Sensitivity Questionnaire (EXAMPLE)

Subject # \_\_\_\_\_ Date: \_\_\_\_\_

**When completing this form please consider your experience over the last 24 hours**

Have your teeth been sensitive ? Y/N     **If NO do not complete any further questions.**

Please make a single vertical mark at the point on the line which represents the degree of overall tooth sensitivity (eg twinges, pain and other sensations in your teeth) that you have experienced **over the last 24 hours**

[figure not shown]
No Sensitivity	_____	Extreme Sensitivity
-------------------	-------	------------------------

For Site use only: \_\_\_\_\_ mm     \_\_\_\_\_ Initials

**In the last 24 hours, have you used any pain killing medications to relieve tooth sensitivity/pain?**

Yes 	No 
------------------------------	-----------------------------

Please rate the **INTENSITY/DURATION/TOLERABILITY/DESCRIPTION** of your overall tooth sensitivity (eg twinges, pain and other sensations in your teeth) experienced over the past 24 hours. Mark the scales below with an “x” to indicate the best description of your sensitivity. Remember you can mark anywhere on the line, including between the descriptive words.

Final v1.0 16 Oct 15

Scorer initials (site staff):

On a scale of 1 to 10 **how bothered** have you been by any tooth sensitivity (eg twinges, pain, ache or other sensations in your teeth) that you have experienced over the last 24 hours (please circle your answer)

Not at all      1      2      3      4      5      6      7      8      9      10      Extremely  
 Bothered

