
## 2 STUDY OBJECTIVES AND ENDPOINTS

**Table 2-1 Study Objectives and Endpoints**

Objectives	Endpoints
Primary	
To characterize the subject-perceived sensitivity protection profile of a 5% NovaMin-containing dentifrice, a 5% KNO 3 -containing dentifrice and a reference fluoride dentifrice during and for 2 weeks post tooth bleaching.	
Daily responses from the tooth sensitivity questionnaire through the study in:-
 
 
• Visual analogue scale (VAS)
 
• Labelled Magnitude scales (Intensity, Duration, Tolerability, Description) - LMS
 
• Bothersomeness score – NRS
 
• Number of subjects who experience tooth sensitivity
 
• Number of subjects who used analgesics to alleviate tooth sensitivity
 

Secondary	
To investigate the ability of a 5% NovaMin-containing dentifrice to reduce self-perceived tooth sensitivity as measured by a subject-completed tooth sensitivity questionnaire compared to a 5% KNO 3 -containing dentifrice and a reference fluoride dentifrice during tooth bleaching.	
Responses from the tooth sensitivity questionnaire completed during tooth bleaching (Visit 2-3) in:-
 
 
• Mean VAS
 
• Mean LMS
 
• Mean Bothersomeness
 
• % tooth sensitivity-free days
 
• % days analgesics used to alleviate tooth sensitivity
 

To investigate the ability of a 5% NovaMin-containing dentifrice to reduce self-perceived tooth sensitivity as measured by a subject-completed tooth sensitivity questionnaire compared to a 5% KNO 3 -containing dentifrice and a reference fluoride dentifrice for 2 weeks from the end of tooth bleaching.	
Responses from the tooth sensitivity questionnaire completed during the 2 weeks post completion of tooth bleaching (Visit 3-4) in:-
 
 
• Mean VAS
 
• Mean LMS
 
• Mean Bothersomeness
 
• % tooth sensitivity-free days
 
• % days analgesics used to alleviate tooth sensitivity.
 

To confirm the tooth whitening efficacy of peroxide tooth bleaching with concurrent, twice daily use of a 5% NovaMin-containing dentifrice, a 5% KNO 3 -containing dentifrice and a reference fluoride dentifrice as measured by VITA Bleachedguide 3D Master.	Change in mean VITA shade score from pre- to post-tooth bleaching (Visit 2-3)
Exploratory	

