#### 6.3.1 Tooth Sensitivity Questionnaire

The tooth sensitivity questionnaire [including VAS and LMS] will be completed by the subject at the screening visit, at Visit 2 (prior to bleaching) to describe the overall tooth sensitivity experienced by the subject on that day. The questionnaire should then be dispensed to the subject to complete at home, in the evening, every day until they complete the study. Thus on the day of Visit 2 the subject should complete 2 questionnaires, one at site and one in the home. Thereafter the subject should complete 1 questionnaire per day at home.

Subjects will indicate whether they have felt tooth sensitivity during the previous 24 hours. Those who indicate they have not felt tooth sensitivity will not be required to complete the rest of the questionnaire. Subjects who indicate they did feel tooth sensitivity will complete the remainder of the questionnaire comprising the VAS, LMS and Bothersomeness numerical rating scale (NRS).

Subjects will rate their overall tooth sensitivity using a 100mm VAS with end anchors of 'No Sensitivity' to 'Extreme Sensitivity'.

The LMS apply psychophysical procedures (magnitude estimation and cross-modality magnitude matching) to condition specific descriptive words relevant to the subject's response ([Gracely et al., 1978](#)). The descriptive words are then aligned along a Visual Analogue Scale (VAS) at distances that reflect the psychological distances between words. These scales have been piloted and validated in a previously reported dentine hypersensitivity trials ([Heaton et al., 2013](#), [Mason et al., 2019](#)). The LMS will be used to rate the intensity, duration, tolerability

Property of Haleon- Confidential

May not be used, divulged, published or otherwise disclosed without the consent of Haleon

and descriptive quality of their tooth sensitivity using the four individual 100 millimetre (mm) LMS.

The study staff will measure the line segment marked-off in mm from bottom to top along the line (for LMS) and from left to right (for the VAS) and record this in the CRF.

The subject will also complete a NRS for bothersomeness for which the subject should circle an appropriate number on the scale.

All questionnaire data shall be recorded in the CRF upon return of completed questionnaire.

All questionnaire data shall be recorded in the CRF.

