#### 8.3.1 Primary Endpoint Analysis

The modified Intent-to-Treat (mITT) population will be used for the primary analyses.

The primary endpoints are:

- Daily VAS scores collected through the study
- Daily LMS scores collected through the study
- Daily Bothersomeness scores collected through the study
- Daily number and % of subjects with a tooth sensitivity-free day through the study
- Daily number and % of subjects with analgesic used to alleviate tooth sensitivity through the study

Property of Haleon- Confidential

May not be used, divulged, published or otherwise disclosed without the consent of Haleon

Each endpoint will be summarized descriptively at Screening and Visit 2 (pre-bleaching) as well as by each relative day within the tooth bleaching and post-tooth bleaching period.

Days within the tooth-bleaching period will be relative to the Visit 2 [at home] result (day 1) up to and including the result recorded on the day prior to Visit 3. Days within the post-tooth bleaching period will be relative to the result following Visit 3 (at home) (day 1) and include any results up to and including the day of Visit 4. The daily mean ( $\pm$  SE) profiles of VAS, LMS and Bothersomeness scores across the study (clearly denoting each period) will be plotted by study product group.

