For the % tooth sensitivity-free days and the % days analgesics used to alleviate tooth sensitivity during the tooth bleaching period, a negative binomial model will be applied to the number of days with the event. Study product and DH diagnosis at screening (yes/no) will be fitted as fixed effects. An offset variable for the number of days the daily question related to tooth sensitivity (Yes/No) was completed during the tooth bleaching period will be included to adjust for missing days in estimating the rates. The back transformed rates for each study product group and ratios between rates will be presented along with 95% CIs.

Each analysis assessing tooth sensitivity during the tooth bleaching period will also be applied to the same tooth sensitivity endpoints during the post-tooth bleaching period.

The tooth sensitivity scores at Visit 2 (prior to bleaching) will not be included in the analyses as a covariate because it is expected that the randomized product group at Screening will have

Property of Haleon- Confidential

May not be used, divulged, published or otherwise disclosed without the consent of Haleon

a causal effect on this outcome. Low tooth sensitivity following tooth bleaching should not be adjusted in the analysis for low tooth sensitivity at Visit 2, as this could be lower in general for subjects randomized to test and reference dentifrice groups at Visit 1.

An ANCOVA model will be applied to analyze the change in the mean VITA Shade score from pre- to post-tooth bleaching (Visit 2-3) with study product as a fixed effect and the mean VITA-Shade color score at screening fitted as a covariate. The least square means (with SE and 95% CI) for each study product will be presented along with the difference (with SE and 95% CI).

The assumption of normality and homogeneity of variance in each parametric test applied (i.e. ANCOVA / MMRM) will be investigated. In case of violation of these assumptions, a suitable non-parametric test will be performed, and results will be provided to support the parametric results.

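### The analgesic item sits behind the No-sensitivity stop, so use on No days cannot reach the analgesic endpoints, and the secondary model counts those days as analgesic-free

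*Combined protocol and SAP*

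**What the plan says.** Section 9.10 (example form) opens with a Yes/No question on sensitivity over the last 24 hours. A subject who answers No reads "If NO do not complete any further questions". The painkiller item, "have you used any pain killing medications to relieve tooth sensitivity/pain", comes later on the form, after the VAS.

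Section 6.3.1 repeats the skip: "Those who indicate they have not felt tooth sensitivity will not be required to complete the rest of the questionnaire". It then lists the remainder as the VAS, the LMS and the bothersomeness scale, without naming the analgesic item.

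Analgesic use appears at two levels of Table 2-1:

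- Primary: "Number of subjects who used analgesics to alleviate tooth sensitivity". Section 8.3.1 restates this as "Daily number and % of subjects with analgesic used to alleviate tooth sensitivity through the study", with no denominator and no rule for skipped items.
- Secondary: the percentage of "days analgesics used to alleviate tooth sensitivity", separately for the bleaching and post-bleaching periods. Section 8.3.2 models the count of event days with a negative binomial model and, to adjust for missing days, includes "An offset variable for the number of days the daily question related to tooth sensitivity (Yes/No) was completed" in the period.

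Three other places bear on the point. Section 4.4.5 tells subjects who take ad hoc medication for sensitivity to note it in this questionnaire. Table 5-1 schedules a medication review at Visits 1 to 4. Section 8.3.7 says that prior and concomitant medications are only listed.

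**The concern.** A subject who takes a painkiller around bleaching, feels nothing and ticks No is stopped before the one item that feeds the analgesic endpoints. The form thus works against Section 4.4.5, which names this questionnaire as the place to note such medication.

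In the secondary model, a day on which the analgesic question was not put adds to the exposure but cannot add an event. Not asked becomes not used. The same day is also credited as sensitivity-free, although the absence of symptoms may be due to the painkiller and not to the dentifrice.

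As built, the analgesic endpoint measures days that were both sensitive and treated. It is tied mechanically to the sensitivity-free-day endpoint and is not a separate piece of evidence about the products.

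**Working it through.** The plan gives no figure for analgesic use, so there is no figure of its own to reproduce on this point. Its one piece of sample-size arithmetic does reproduce (90 × 0.98 = 88.2, stated as about 88), but nothing here depends on it.

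**Definitions.** All three quantities are assumptions; the documents give none of them.

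- s = share of answered days with No to sensitivity
- a = share of sensitive days with analgesic use
- f = share of No days with analgesic use (preventive or masking)

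**Formulas, using the Section 8.3.2 offset as denominator.**

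- Recorded analgesic-day rate = (1 − s) × a
- Rate if the item were asked every day = (1 − s) × a + s × f
- Share of use days missed = s × f / [(1 − s) × a + s × f]

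**Secondary endpoint, equal f in both arms.** Take s = 0.7 (test) and 0.5 (reference), with the same a in both. The recorded ratio is 0.30 / 0.50 = 0.60 whatever a and f are.

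| a | f | Rate if asked daily, test / reference | Ratio | Share missed, test / reference |
|---|---|---|---|---|
| 0.2 | 0 | 0.060 / 0.100 | 0.60 | 0% / 0% |
| 0.2 | 2% | 0.074 / 0.110 | 0.67 | 19% / 9% |
| 0.2 | 5% | 0.095 / 0.125 | 0.76 | 37% / 20% |
| 0.2 | 10% | 0.130 / 0.150 | 0.87 | 54% / 33% |
| 0.1 | 2% | 0.044 / 0.060 | 0.73 | 32% / 17% |
| 0.1 | 5% | 0.065 / 0.075 | 0.87 | 54% / 33% |
| 0.1 | 10% | 0.100 / 0.100 | 1.00 | 70% / 50% |

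Here the skip exaggerates the difference between arms, because more use is missed in the arm with more No days.

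**Unequal f.** With a = 0.2, f = 2% in test and f = 10% in reference, the rates if asked daily are 0.060 + 0.7 × 0.02 = 0.074 and 0.100 + 0.5 × 0.10 = 0.150. The ratio is 0.49, so the recorded 0.60 now understates the difference.

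**Equal s.** With s = 0.5 in both arms and equal f, the ratio is 1.00 either way, but both rates are understated (for a = 0.2 and f = 5%, 0.100 recorded against 0.125).

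**Sensitivity-free days.** The share of all answered days that is credited as sensitivity-free despite analgesic use is s × f. At f = 5% this is 3.5 percentage points for s = 0.7 and 2.5 points for s = 0.5. Over 7 bleaching days that is 0.7 × 0.05 × 7 = 0.245 and 0.5 × 0.05 × 7 = 0.175 days per subject.

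**Primary daily percentage.** Take 30 responders per arm and a = 0.2.

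- s = 0.5: 15 subjects are asked and 3 report use. That is 3/30 = 10% of responders or 3/15 = 20% of those asked.
- s = 0.7: 9 are asked and 1.8 are expected to report use. That is 1.8/30 = 6% of responders or 1.8/9 = 20% of those asked.

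The unstated denominator alone decides whether the arms read as 6% against 10% or as 20% against 20%.

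**The case against.** The strongest reply is that the endpoint concerns relief, not prevention. Table 2-1, Section 8.3.1 and the form all speak of use to alleviate or relieve sensitivity, and both questions look back 24 hours. A subject who felt and treated sensitivity in that window should tick Yes and so reach the item. For relief use, a No day is ordinarily a day without use, and all answered days are a natural denominator. This stands, and it limits the gap to preventive use and to sensitivity so well masked that No was ticked.

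The stakes are also modest. Primary endpoints are summarised descriptively, there is no formal success criterion, and the sample size rests on feasibility. The form is labelled an example, and Section 6.3.1 does not name the analgesic item among those skipped. That last point shows an inconsistency to settle more than it defends the form, because the subject follows the printed instruction.

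Three stronger readings are tempting but unsupported:

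- A reader might infer that such use is never recorded. The visit medication reviews may capture it. What is missing is any route from those records to the endpoints, since they are only listed.
- A reader might infer that the primary percentage also counts these subjects as analgesic-free. The count omits them, but Section 8.3.1 does not say whether the percentage treats them as non-users or leaves them out.
- A reader might infer that the bias pulls the arms together, because less protected subjects would pre-medicate more. Nothing in the documents supports that pattern, and with equal use on No days the effect goes the other way.

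**Conclusion.** The structural gap is real. Under the printed form, analgesic use on a day answered No cannot reach the questionnaire-based endpoints. In the secondary model those days enter the offset as analgesic-free, and they also count as sensitivity-free. For the primary percentage the finding is narrower: the denominator is not defined.

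The size depends entirely on f, which the documents do not give. If f is zero, no use is missed and the secondary rates are unaffected. In the illustrations with equal f between 2% and 10%, the ratio moves from a recorded 0.60 to between 0.67 and 1.00; with unequal f it can move to 0.49. These figures show sensitivity to assumptions and do not estimate a bias. The true effect may be small, and its direction between arms cannot be determined. Sample size is not affected. This is a cheap improvement worth making, because data not collected on the day cannot be fully recovered later.

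**What to change.** 1. **Form.** Place the analgesic Yes/No item before the skip so that it is answered every day. Word it to cover use to prevent or to relieve tooth sensitivity or pain, and record the two purposes separately so that the endpoint on alleviation is kept. Moving the item without rewording it would not be enough: a pre-emptive user could still truthfully answer No to a question about relief.
2. **Section 6.3.1.** Name the analgesic item and say that it is completed daily, in line with the form.
3. **Sections 8.3.1 and 8.3.2.** Use days (or subjects, for the daily summary) with the analgesic item answered as the denominator of the primary percentage and as the offset of the secondary analgesic model. Keep the present offset for sensitivity-free days.
4. **Supportive summary.** Report sensitivity-free days also without crediting days with analgesic use.
5. **If forms are already in use.** State the skipped-day rule and the denominator for both endpoints before unblinding, and cross-check the concomitant-medication records at the blinded data review (Section 8.2.1).

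The cost is one extra tick box per symptom-free day, a purpose tick on days with use, and a few lines of text in the protocol.
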